**Table TTT. Injection Site Reactions** 

Kind of	Maximum	Placebo	4P004	4P004	4P004	4P004	4P004
Reaction	Toxicity	(pooled)					(pooled)
	Grade	(N=XX)	(N=XX)	(N=XX)	(N=XX)	(N=XX)	(N=XX)
Any Kind	Any Grade	XX (XX.X%)					
	1 Mild	XX (XX.X%)					
	2 Moderate	XX (XX.X%)					
	()						
Tenderness	Any Grade	XX (XX.X%)					
	1 Mild	XX (XX.X%)					
	2 Moderate	XX (XX.X%)					
	()						
Erythema	Any Grade	XX (XX.X%)					
	1 Mild	XX (XX.X%)					
	2 Moderate	XX (XX.X%)					
	()						
()	• •						

#### 12.2.6 Serious adverse events

A listing of all SAEs will be provided.

#### **Listing LLL. Serious Adverse Events**

#### 12.2.7 Deaths

If any subject dies during the study, relevant information will be supplied in a data listing, and appropriate SAE narratives.

#### **Listing LLL. Deaths**

#### 12.3 Target knee pain

The target knee pain, evaluated on a 0-10 scale, is measured as follows:

Visit	Timepoint	Table
Screening	(mean of the last 48 hours)	-
Visit 2	(mean of the last 48 hours)	2,3
	Pre-Dose	1
	1h Post-Dose	1
	2h Post-Dose	1
	3h Post-Dose	1
	4h Post-Dose	1
	5h Post-Dose	1
	6h Post-Dose	1
	24h Post-Dose (mean of the last 24 hours)	1,2,3
Visit 3	(mean of the last 24 hours)	2,3
	Day 3 (mean of the last 24 hours)	3
	Day 4 (mean of the last 24 hours)	3
	Day 5 (mean of the last 24 hours)	3
	Day 6 (mean of the last 24 hours)	3
	Day 7 (mean of the last 24 hours)	3
	Day 8 (mean of the last 24 hours)	3
Phone Call 2	Day 15 (mean of last 48 hours)	2
	Day 22 (mean of last 48 hours)	2
	Day 29 (mean of last 48 hours)	2

In the tables of this section, in addition to the values, the change from Baseline will be added, with the standard summary statistics and the number of subjects with an aggravation since the Baseline.

In case of two different measures on the same day, the value of the diary will prevail.

The pain will be presented in three summary tables:

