## 8.1.6 Target knee pain

The participants will also assess target knee pain using a numerical rating scale (NRS), 11 points (0-10) to assess pain of the target knee as outlined in section 1.2:

- At screening (as a mean of the previous 2 days)
- At D1: T0-4h as a mean of the previous 2 days and currently and every hour after T0 up to T0+6h
- At D2 before hospital discharge: assessment from IA injection to hospital discharge
- From D3 to D8 Visit: daily, assessment from the previous 24 hours
- From D15 to D29: weekly assessment based on pain during the previous 2 days.

A pre-paid and pre-printed envelope will be given to the participant on D8 visit for mailing these records to the Investigator.

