## Target knee pain

Results of the NRS will be summarized by visit, maximum value with corresponding visit and will be presented per participant and treatment group.

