### Events NOT meeting the AE definition

- Medical or surgical procedure (e.g., endoscopy, appendectomy): the condition that leads to the procedure is the AE.
- Situations in which an untoward medical occurrence did not occur (social and/or convenience admission to a hospital).
- Anticipated day-to-day fluctuations of pre-existing disease(s) or condition(s) present or detected at the start of the study that do not worsen.
- Surgery planned prior to informed consent to treat a pre-existing condition that has not worsened

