### 9 General Principles for Statistical Analysis

Data will be summarized using classical descriptive statistics for the following groups:

- pooled placebo (i.e. participants receiving placebo in any cohort),
- each 4P004 dose level,
- unplanned doses if any (see below),
- 4P004 overall

A group "All" (Placebo + 4P004 overall) will be added if explicitly mentioned.

Categorical data will be presented using counts and percentages of subjects, while continuous variables will be presented using the mean, standard deviation, median, minimum, maximum, and number of observations with non-missing values. The coefficient of variation [%CV] will be provided for PK parameters.

The safety evaluation will be based upon the review of the individual values and descriptive statistics. No statistical significance tests will be performed on safety data.

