#### 16 References

ICH Guidance Topic E9 "Statistical Principles for Clinical Trials"

# 17 Tables, Figures & Listings in CSR Section 14

The following tables will be included in the report either in the text or in a dedicated chapter reporting all tables but not included in the text.

Туре	Number	Title	Population
Table	1.1	Participant disposition	All
Table	1.2	Deviations by Category	Safety
Listing	1.2.1	Major Deviations	Safety
Table	1.3	Demographics and Baseline Characteristics	Safety
Table	1.4	Other Baseline Characteristics	Safety
Table	1.5.1	Pain killers started and ended before treatment	Safety
Table	1.5.2	Other medications started and ended before treatment	Safety
Table	1.6	Medical History by SOC	Safety
Table	2.1	Pain killers started before treatment and continuing at IMP injection	Safety
Table	2.2	Pain killers started during treatment	Safety
Table	2.3	Other medications started before treatment and continuing at IMP injection	Safety
Table	2.4	Other medications during treatment	Safety
Table	3.1	Overview of TEAEs	Safety
Table	3.1.1	TEAEs by SOC and PT	Safety
Table	3.1.2	TEAEs by SOC, PT and Toxicity Grade	Safety
Table	3.1.3	TEAEs by SOC, PT and Relationship to Study Drug	Safety
Table	3.2	Treatment-Emergent AESIs by SOC and PT	Safety
Table	3.2.1	Treatment-Emergent AESIs by SOC, PT and Toxicity Grade	Safety
Listing	3.2.2	Treatment-Emergent AESIs	Safety
Table	3.3	Injection Site Reactions	Safety
Listing	3.4	Serious Adverse Events	Safety
Listing	3.5	Deaths	Safety
Table	4.1	Target Knee Pain from Pre-Dose to 24h Post-Dose	Safety
Table	4.2	Target Knee Pain from Visit 2 to End of Study	Safety
Table	4.3	Target Knee Pain from Visit 2 to Day 8	Safety
Table	5.0	Weight over Time	Safety
Table	5.1	Systolic Blood Pressure over Time	Safety
Table	5.2	Diastolic Blood Pressure over Time	Safety
Table	5.3	Heart Rate over Time	Safety
Table	6.1	ECG: Heart Rate over Time	Safety
Table	6.2	ECG: PR over Time	Safety
Table	6.3	ECG: QRS over Time	Safety
Table	6.4	ECG: QT over Time	Safety
Table	7.1	Hematology over Time	Safety
Table	7.1.1	Hematology PCSA over Time	Safety
Table	7.2	Chemistry over Time	Safety
Table	7.2.1	Chemistry PCSA over Time	Safety
Table	7.3	Glycemia over Time	Safety
Table	8.1	Plasma Concentrations over Time	PK
Figure	8.1.0.3	Plasma Concentrations over Time by Subject -	PK
Figure	8.1.1	Plasma Concentrations over Time by Subject -	PK
Figure	8.1.2	Plasma Concentrations over Time by Subject -	PK
Figure	8.1.3	Plasma Concentrations over Time by Subject -	PK

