# 18 Listings in CSR Section 16.2

The following listings will be included in section 16.2 of the CSR.

Туре	Number	Title	Population
Listing	16.2.1	Demographics and Disposition	Safety
Listing	16.2.2	Prior and Concomitant Medications	Safety
Listing	16.2.3	Medical History	Safety
Listing	16.2.4	Serology	Safety
Listing	16.2.5	Knee X-Ray and Kellgren-Lawrence Grade	Safety
Listing	16.2.6	Failed Inclusion/Exclusion Criteria	Safety
Listing	16.2.7	IMP Injection	Safety
Listing	16.2.8	Deviations	Safety
Listing	16.2.9	Adverse Events	Safety
Listing	16.2.10	Knee Pain Assessments	Safety
Listing	16.2.11	Height, Weight and BMI	Safety
Listing	16.2.12	Vital Signs	Safety
Listing	16.2.13	ECG	Safety
Listing	16.2.14	Hematology	Safety
Listing	16.2.15	Chemistry	Safety
Listing	16.2.16	Glycemia	Safety
Listing	16.2.17	Exploratory Sample Collection	Safety
Listing	16.2.18	Plasma Concentrations	Safety
Listing	16.2.19	PK Parameters	Safety
Listing	16.2.20	Visits	Safety
Listing	10.2.20	VISITS	Sarety

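### The protocol promises each participant's highest knee-pain score with its visit, but the SAP neither derives nor tabulates it, so flares occurring at any time are not summarised by dose

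*SAP*

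**What the plan says.** Protocol 10.1.4 (Target knee pain) states: "Results of the NRS will be summarized by visit, maximum value with corresponding visit and will be presented per participant and treatment group".

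Protocol 8.1.6 sets a dense rating schedule. On D1 there is a pre-injection score and then one "every hour after T0 up to T0+6h". A further rating follows at discharge on D2, then daily ratings to D8 and weekly ratings from D15 to D29. Counting the Visit 3 and Day 8 ratings once, that is 6 + 1 + 6 + 3 = 16 distinct post-injection timepoints.

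SAP 12.3 assigns these timepoints to tables: "The pain will be presented in three summary tables". Each gives the value and the change from baseline, "with the standard summary statistics and the number of subjects with an aggravation since the Baseline". SAP 9 defines the standard statistics: "continuous variables will be presented using the mean, standard deviation, median, minimum, maximum, and number of observations with non-missing values". In the table list (SAP 17) the last knee-pain entry is Table 4.3, "Target Knee Pain from Visit 2 to Day 8". SAP 18 adds Listing 16.2.10, "Knee Pain Assessments".

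**The concern.** Target knee pain is named in the primary safety endpoint (Protocol 3.2.1), and Protocol 2.3 states that there are no human safety data after intra-articular injection. Pain in the injected knee is therefore a central local-tolerability question for this route.

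Pain after an injection can be brief and can come at different times in different people. The useful result at each dose is how many participants had a flare at any time and how large it was. A set of separate timepoint summaries does not give that, because nothing links one row to the next within a participant. With six active participants per cohort and no significance tests, the descriptive tables are the analysis, so a summary left out of them is a result not reported.

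**Working it through.** **1. Protocol against SAP.** A maximum that carries a corresponding visit has to be taken across visits within a participant. The maximum in SAP 9 is taken across participants within a timepoint, so it is a different quantity.

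- SAP 9.4 (derived variables): baseline, epochs and PK parameters; no maximum NRS.
- SAP 12.3: three tables, all by timepoint or day.
- SAP 17: Tables 4.1 to 4.3 and no other knee-pain output.
- SAP 18: Listing 16.2.10, planned as a listing of the assessments.

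The SAP gives no reason for leaving the maximum out. The plan states no figure on this point, so there is none to reproduce.

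**2. Can the timepoint tables stand in for it?** From the documents: 6 active participants per cohort and 6 hourly ratings. Assumed: baseline 3 for everyone and a flare of +4.

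- Case A: each of the six participants flares once, each at a different hour.
- Case B: one participant flares at all six hours and the other five never do.

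In both cases every hourly row contains one change of +4 and five of 0:

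- mean change = 4/6 = 0.67
- SD = √[(16 − 6 × 0.667²)/5] = √2.667 = 1.63
- median change = 0
- highest score = 3 + 4 = 7
- aggravated = 1/6

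| | Case A | Case B |
|---|---|---|
| Each hourly row (mean change; highest score; aggravated) | 0.67; 7; 1/6 | 0.67; 7; 1/6 |
| Participants with a flare at any hour | 6/6 | 1/6 |
| Mean of participants' maximum change | 24/6 = 4.0 | 4/6 = 0.67 |

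The rows are equally indistinguishable for other flare sizes. With +3 the mean change per row is 0.50, and the mean of the participants' maxima is 3.0 against 0.5. With +5 the figures are 0.83, and 5.0 against 0.83.

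**3. Does this need perfectly spread flares?** Suppose each of six participants flares once at a random timepoint out of T. Let k be the number of timepoints hit twice. The probability that no timepoint holds more than two of the six flares is

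Σ (k = 0 to 3) C(T,k) · C(T−k, 6−2k) · 6!/2^k ÷ T^6.

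- T = 6: (720 + 10,800 + 16,200 + 1,800)/46,656 = 0.63
- T = 16: (5,765,760 + 7,862,400 + 1,965,600 + 50,400)/16,777,216 = 0.93

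So even when all six flare, the most affected row will usually show no more than 2 of 6.

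**4. How noisy is a maximum?** Simulation of a stable participant: true level 3 to 7, ratings rounded to whole points on 0-10, baseline rated with the same error, within-person SD assumed.

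| Within-person SD | Rise ≥ 1, one timepoint | Rise ≥ 2, one timepoint | Maximum rise ≥ 2 over six ratings |
|---|---|---|---|
| 0.7 | 31% | 7% | 24% |
| 1.0 | 36% | 15% | 42% |
| 1.5 | 41% | 24% | 58% |

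A count based on a 2-point cut is therefore hard to interpret without a comparison group rated on the same schedule.

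**The case against.** Several points on the other side stand and limit the finding.

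- **The tables are not means alone.** A reader might infer that flares vanish from the output. They do not: every row carries the minimum and maximum, and in the example every hourly row shows a score of 7, a largest change of +4 and 1/6 aggravated. Only the mean is diluted.
- **The individual data are planned.** Listing 16.2.10 covers about 33 participants (4 × 8, plus the ninth in cohort 3, SAP 9.3), and SAP 9 bases the safety evaluation partly on individual values. Each maximum and its visit could be worked out by hand. That largely meets the per-participant part of the protocol's promise, but not the part by treatment group.
- **Clinically important pain has other routes.** Knee pain can be an AE, and TEAEs are counted by participant, preferred term and grade. Injection-site reactions are shown by maximum grade, and painkillers started during treatment are tabulated. It would go too far to say that a dose effect on pain must be missed. These routes depend on reporting or medication use, however, and do not summarise the NRS.
- **The aggravation count breaks no protocol rule.** It has no stated minimum size, and a reader might set it against the protocol's exclusion of "Anticipated day-to-day fluctuations of pre-existing disease(s) or condition(s) present or detected at the start of the study that do not worsen". That text defines what is not an AE. It does not govern a descriptive count of NRS rises, which the SAP never calls AEs and shows beside pooled placebo.
- **A 2-point cut on the maximum does not remove noise.** Over six ratings it misclassifies a stable participant 24-58% of the time, against 31-41% for any rise at one timepoint. This counts against making a cut-off the main result. It does not count against the promised maximum.

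**Conclusion.** The concern holds as a reporting gap between protocol and SAP. The per-participant maximum with its visit, by treatment group, is promised in Protocol 10.1.4 and has no derivation or table in the SAP. As a result the number and size of knee-pain flares at any time are not summarised by dose. The planned rows can be identical when 6/6 participants flared and when 1/6 did.

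The gap itself rests on the documents alone. The baseline of 3, the flare sizes, their timing and the within-person SDs are assumptions used to show its consequence; none is a trial figure. Cases A and B are deliberately extreme, and the random-timing calculation shows that the problem is not confined to them.

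The importance is moderate. The data are collected and listed, and no hypothesis test depends on them. The omission nevertheless concerns the main NRS result for the injected joint.

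**What to change.** Add one derivation and one table to SAP 12.3, and list the table in SAP 17. Per participant, and summarised for each 4P-004 dose and pooled placebo, give:

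- the maximum post-injection NRS;
- the time or visit at which it occurred;
- the maximum increase from the matching baseline (the current pre-injection score for the hourly ratings, the 48-hour mean at Visit 2 for later ones).

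Report these separately for 1-6 h, D2-D8 and D15-D29, so that windows with different numbers of ratings are not mixed. Show the distribution of the maximum increase as the main result. Any count above a cut-off should be secondary, fixed by the sponsor before unblinding, and read only against placebo on the same rating schedule. If the sponsor prefers not to add the table, the SAP should state the departure from Protocol 10.1.4 and the reason.

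The cost is SAP wording and one more table; no new data are needed. The drawback is that a maximum rises with the number of ratings even in stable participants, and pooled placebo, planned at 4 × 2 = 8 participants, is a small reference group.

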#### Table TTT. Target Knee Pain from Pre-Dose to 24h Post-Dose

(timepoints marked « table 1 » in the list above)

#### Table TTT. Target Knee Pain from Visit 2 to End of Study

(timepoints marked « table 2 » in the list above)

For this table, the baseline will be the mean of the last 48 hours collected at Visit 2 or, if not available, the Screening value.

#### Table TTT. Target Knee Pain from Visit 2 to Day 8

(timepoints marked « table 3 » in the list above)

This table will be presented by actual day of pain, whatever scheduled day the measure has been assigned to.

#### 12.4 Weight

Weight will be presented at Baseline and at Visit 3, with the change from Baseline.

#### **Table TTT. Weight over Time**

#### 12.5 Vital Signs

The vital signs are systolic blood pressure, diastolic blood pressure and heart rate. They are measured as follows:

Visit	Timepoint
Screening	-
Visit 2	Pre-Dose
	1h Post-Dose
	2h Post-Dose
	4h Post-Dose
	8h Post-Dose
	12h Post-Dose
	24h Post-Dose
Visit 3	_

The following will be presented for each vital sign:

- value (mean, SD, etc.)
- absolute change from baseline (mean, SD, etc.)
- PCSA (frequencies and percentages)

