## 3.2 Endpoints

#### 3.2.1 Primary endpoints

- Number of Adverse events (AEs), serious AEs (SAEs) (Common Terminology Criteria Adverse Events [CTC-AE]) from ICF signature to D29, including target knee pain and tenderness, erythema, swelling, local pain at injection site.
- Vital signs from D-7 to D8, ECG from D-7 to D1: Mean change, number of Potentially Clinically Significant Abnormality (PCSA), Percentage of participants with PCSA
- Laboratory changes (Red Blood Cells (RBC), White Blood Cells (WBC), Hemoglobin (Hb), platelets, alanine transaminase (ALT), aspartate transaminase (AST), glycemia, amylasemia, creatinin clearance) from D-7 to D8: Mean changes number of PCSA, Percentage of participants with PCSA.

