### Vital signs

Individual results of vital signs that meet PCSA criteria to be defined in the SAP will be listed and summarized. Observed values and changes from Baseline in vital sign measurements (systolic and diastolic blood pressure and heart rate,) will be summarized. All vital signs data will be provided in the data listings.

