**Table TTT. Systolic Blood Pressure over Time** 

mmHg	Placebo	4P004	4P004	4P004	4P004	4P004
	(pooled)					(pooled)
	(N=XX)	(N=XX)	(N=XX)	(N=XX)	(N=XX)	(N=XX)
Baseline						
Value						
n	XX	XX	XX	XX	XX	XX
mean (SD)	XX (XX)					
()						
1h Post-Dose						
Value						
n	XX	XX	XX	XX	XX	XX
mean (SD)	XX (XX)					
()						
Change from BL						
n	XX	XX	XX	XX	XX	XX
mean (SD)	XX (XX)					
()						
PCSA						
≤ 95 + decrease from baseline ≥ 20	XX (XX.X%)					
≥ 160 + increase from baseline ≥ 20	XX (XX.X%)					
No PCSA	XX (XX.X%)					
()						

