### **Table TTT. Chemistry over Time**

### **Table TTT. Chemistry PCSA over Time**

Glycemia is measured as follows:

Visit	Timepoint	Method
Screening	-	Blood
Visit 2	Pre-Dose	Blood & Glucometer
Visit 2	1h Post-Dose	Glucometer
Visit 2	2h Post-Dose	Blood
Visit 2	4h Post-Dose	Blood
Visit 2	6h Post-Dose	Glucometer
Visit 2	8h Post-Dose	Blood
Visit 2	10h Post-Dose	Glucometer
Visit 2	12h Post-Dose	Blood
Visit 2	16h Post-Dose	Blood
Visit 2	24h Post-Dose	Glucometer
Visit 3	-	Blood & Glucometer

In order to obtain one value per scheduled timepoint:

- The baseline value will be selected as the last measure before IMP injection. If there are such two measures (same time, different method), then Blood will be selected.
- Post-baseline, if there are two measures for a scheduled timepoint, Blood will be selected.
- Additional samples vs. scheduled samples will not be analyzed, unless they are the baseline.

The values will be reported over time (Baseline, 1h Post-Dose to 24h Post-Dose) with the same template as Vital Signs.

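### No planned summary table gives the share of participants with a vital-sign or glycemia PCSA over the endpoint window, because the SAP tabulates these only timepoint by timepoint

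*SAP*

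**What the plan says.** Protocol 3.2.1 sets the primary endpoints. For vital signs it asks for the mean change and for the "number of Potentially Clinically Significant Abnormality (PCSA), Percentage of participants with PCSA". For laboratory values, glycemia included, the window and measures are "from D-7 to D8: Mean changes number of PCSA, Percentage of participants with PCSA". Protocol 10.1.4 adds, for vital signs: "Individual results of vital signs that meet PCSA criteria to be defined in the SAP will be listed and summarized". Its laboratory paragraph makes the same promise. Neither paragraph says whether the summary is per timepoint or per participant.

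The SAP fills this in as follows.

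- **Section 12.5** presents, for each vital sign, the value, the change from baseline and "PCSA (frequencies and percentages". The shell for systolic pressure puts rows such as "≤ 95 + decrease from baseline ≥ 20" inside a timepoint block.
- **Section 12.7, glycemia:** "The values will be reported over time (Baseline, 1h Post-Dose to 24h Post-Dose) with the same template as Vital Signs". Visit 3 glucose is reported with Chemistry. Samples beyond the scheduled ones are left out of the analysis unless they serve as baseline.
- **Section 17** titles Tables 5.1 to 5.3 (vital signs) and 7.3 (glycemia) as over-time tables. The PCSA-only tables (7.1.1 and 7.2.1) cover hematology and chemistry and are also over time.
- **Section 18** plans individual listings of vital signs (16.2.12) and glycemia (16.2.16).
- **Section 19** gives the PCSA thresholds but no participant-level derivation.

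**The concern.** The endpoint asks for one share of participants per treatment group over a stated window. The SAP produces a series of percentages, one per scheduled time. A row showing one affected participant at 1 h and another showing one at 2 h do not say whether this is the same person. From the summary tables alone, a reader comparing a dose level with pooled placebo could not separate one participant with repeated abnormalities from several participants with one each.

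Several choices also stay open. These are how the low and high criteria are combined, whether Visit 3 counts, and what happens to unscheduled glucose values. If they are not written down before lock, whoever produces the number will make them with the data in view.

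**Working it through.** **Plan's own figure.** 4 cohorts × (6 active + 2 placebo) = 32, as stated in the protocol synopsis. This gives 6 per dose level, 4 × 6 = 24 on pooled 4P-004 and 4 × 2 = 8 on pooled placebo.

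**Scheduled post-dose times.**
- Vital signs (SAP 12.5): 1, 2, 4, 8, 12 and 24 h, and Visit 3 = 7.
- Glycemia in Table 7.3 (SAP 12.7): 1, 2, 4, 6, 8, 10, 12, 16 and 24 h = 9. Visit 3 glucose is in another table.

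**What the rows determine.** Let a group have n participants, and let c_j of them meet a given criterion at time j. The number affected at least once, A, satisfies

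max(c_j) ≤ A ≤ min(n, Σc_j).

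The lower limit applies when the same people recur, the upper when there is as little overlap as possible. The rows cannot say where A lies between them.

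**Illustration (assumed pattern).** Exactly one participant meets the criterion at every post-dose time, so max(c_j) = 1 and Σc_j is 7 or 9.

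| Group | n | Vital signs, 7 times | Glycemia, 9 times |
|---|---|---|---|
| One dose level | 6 | 1/6 (16.7%) to 6/6 (100%) | 1/6 (16.7%) to 6/6 (100%) |
| Pooled placebo | 8 | 1/8 (12.5%) to 7/8 (87.5%) | 1/8 (12.5%) to 8/8 (100%) |
| Pooled 4P-004 | 24 | 1/24 (4.2%) to 7/24 (29.2%) | 1/24 (4.2%) to 9/24 (37.5%) |

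**A milder pattern.** With one participant affected at each of only two times, A in a dose group of 6 lies between 1/6 (16.7%) and min(6, 2)/6 = 2/6 (33.3%). If the criterion is met at no time or at one time only, the limits coincide and the planned rows already give the exact share.

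**The other measure.** The number of PCSA values at scheduled times is Σc_j, so it can be added up from the rows by hand. The share of participants cannot.

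**Where the problem does not arise.** The ECG has one scheduled post-dose time (12 h). Hematology and chemistry other than glucose have one (Visit 3). For these, the by-timepoint percentage already is the share with any scheduled post-dose PCSA.

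**Outputs checked.** Among Tables 5.1 to 5.3, 7.3, 7.1.1 and 7.2.1, none is described with an any-post-dose row for vital signs or glycemia.

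**The case against.** The protocol never uses the words any post-dose, so a count and percentage at each timepoint is a possible literal reading of the endpoint. The shell is only a template with continuation marks, which do not rule out an overall row. Both points are true. But no SAP text or table title plans such a row, and seven or nine separate percentages do not make one share of participants over D-7 to D8.

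The stronger counter-argument concerns importance, and much of it stands. A reader might infer any of the following, and the documents support none of them.

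- **That the planned outputs as a whole cannot separate one person from many.** This holds for the summary tables only. Listings 16.2.12 and 16.2.16 carry individual values, both documents base the safety evaluation partly on review of individual values, and groups of about 6 can be counted by hand.
- **That the listing promised in the protocol is missing.** No PCSA-only listing is indexed, but the individual values are listed. Only the marking of those that meet a criterion is unplanned.
- **That low glucose would go unseen at participant level.** Hypoglycemia is an adverse event of special interest. Once reported as such, it appears in SAP 12.2.4 with participants, event counts and a listing.
- **That dose tolerability turns on this number.** The maximum tolerated dose is defined by dose-limiting toxicities. Adverse events come first among the primary endpoints, and no significance tests are planned on safety data.

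The full 16.7% to 100% range also depends on a constructed pattern. With few abnormalities it narrows or vanishes.

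**Conclusion.** The gap is real and modest. Followed as written, the SAP does not deliver one of the named primary safety measures in any summary table for vital signs or glycemia, and the planned rows cannot be combined to give it. In a dose group of 6 the uncertainty can be nil, when a criterion is met at no more than one time, or as wide as 16.7% to 100%, when one participant is abnormal at every time.

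For glycemia the gap is slightly larger. The endpoint window runs to D8, but Table 7.3 stops at 24 h. Protocol 8.5.2 calls for extra glucose tests after low planned values or symptoms, and SAP 12.7 leaves those results out of the summary. A participant whose only low value came from such a test would not appear in the glycemia PCSA rows.

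This rests on planned group sizes. SAP 9.3 reports a ninth participant in cohort 3 and a possible separate arm for unplanned doses, so the final denominators may differ slightly. It also reads the protocol's share of participants as one figure per group over the stated window.

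**What to change.** Amend SAP 12.5 and 12.7 before database lock.

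1. Define a participant-level flag for any post-dose PCSA, by criterion and direction, from injection through Visit 3. No exclusion for abnormality already present at baseline is needed for vital signs, since every vital-sign criterion in SAP 19 already requires a change from baseline.
2. Add one block to Tables 5.1 to 5.3 and 7.3 with n (%) of participants with at least one post-dose PCSA, and the number of PCSA values. SAP Table 3.1 already shows subjects beside event counts, and Table 3.3 uses maximum grade per participant.
3. For glycemia, include Visit 3 glucose in the flag. Either count unscheduled post-dose values or show them on a separate line, and say which.
4. Mark PCSA values in Listings 16.2.12 and 16.2.16, so that the protocol's commitment to list them is met.
5. Report the block alongside the by-timepoint rows and the other primary measures. It should not replace them, because that would alter the endpoint set in Protocol 3.2.1.

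The cost is a few lines of SAP text, one block in four tables and a marker in two listings. No new data are needed.
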